6.5.2.5 Nephritis/Renal Failure

Management guidelines for patients experiencing nephritis are as follows:

- Grade 1 nephritis
 - No specific therapy required; close monitoring of renal function
- Grade 2 nephritis
 - Hold pembrolizumab and margetuximab
 - Consider nephrology consultation and renal biopsy to confirm interstitial nephritis.
 - Begin corticosteroids: 1 to 2 mg/kg of oral prednisone or equivalent, per day divided twice daily
 - Taper over 4 weeks as clinically indicated
 - Resume pembrolizumab and margetuximab administration at next scheduled dose if:

- Nephritis resolves to \leq Grade 1 within 14 days with or without treatment
- Grade 3 and 4 nephritis
 - Permanently discontinue pembrolizumab and margetuximab
 - Consider hospitalization, nephrology consultation, and renal biopsy to confirm interstitial nephritis
 - Begin corticosteroids: 2 to 4 mg/kg of oral or IV prednisone or equivalent, per day divided twice daily
 - Taper over 4 weeks as clinically indicated

6.5.2.6 Immune-Mediated Hypophysitis

Management guidelines for patients experiencing hypophysitis are as follows:

- Grade 2 or 3 hypophysitis documented on MRI
 - Hold pembrolizumab and margetuximab
 - Consult endocrinologist
 - Consider hospitalization
 - Begin short course of high dose IV corticosteroids: e.g., methylprednisolone 2-4 mg/kg IV (or equivalent) divided twice daily
 - Initiate hormonal replacement as indicated
 - Pembrolizumab and margetuximab combination treatment may be resumed as allowed by protocol when
 - Endocrinopathy is controlled with appropriate replacement therapy
 - Corticosteroid dose reduced to \leq 10 mg prednisone or equivalent per day
 - Repeat brain MRI as clinically indicated
- Grade 4 hypophysitis
 - Permanently discontinue pembrolizumab and margetuximab.

6.5.2.7 Thyroid Toxicity

Thyroid disorders can occur at any time during treatment with pembrolizumab. Monitor patients for changes in thyroid function per protocol and as indicated based on clinical evaluation and for clinical signs and symptoms of thyroid disorders. Isolated hypothyroidism may generally be managed with replacement therapy without treatment interruption and without corticosteroids, and a suggested treatment guideline for hyperthyroidism is described below:

- Grade 1 hyperthyroidism
 - No specific therapy required
- Grade 2 hyperthyroidism
 - Hold pembrolizumab and margetuximab
 - Consider starting oral corticosteroid therapy
 - Resume pembrolizumab and margetuximab if corticosteroid dose is reduced to ≤ 10 mg prednisone or equivalent per day and stable on hormone replacement therapy (if necessary).
- Grade 3 or 4 hyperthyroidism
 - Hold pembrolizumab and margetuximab
 - Consider hospitalization and consulting endocrinologist
 - Begin IV corticosteroids such as methylprednisolone 2-4 mg/kg IV (or equivalent) divided twice daily
 - Initiate hormonal replacement as necessary
 - May consider restarting pembrolizumab and margetuximab with complete resolution or stable on hormone replacement therapy within 14 days

6.5.2.8 Type 1 Diabetes Mellitus

The following guidelines should be followed for diabetes mellitus (if new onset, including diabetic ketoacidosis [DKA]) or \geq Grade 3 Hyperglycemia, if associated with ketosis (ketonuria) or metabolic acidosis (DKA).

- For **T1DM** or **Grade 3-4** Hyperglycemia
- Insulin replacement therapy is recommended for Type I diabetes mellitus and for Grade 3-4 hyperglycemia associated with metabolic acidosis or ketonuria.
- Evaluate patients with serum glucose and a metabolic panel, urine ketones, glycosylated hemoglobin, and C-peptide.

6.5.2.9 Other Immune-Related AEs

- Intolerable/persistent Grade 2
 - Hold pembrolizumab and margetuximab
 - Based on the type and severity of AE, administer corticosteroids
 - Ensure adequate evaluation to confirm etiology and/or exclude other causes

- Grade 3
 - Hold or discontinue pembrolizumab and margetuximab based on the type of event
 - Discontinuation is required for AEs such as, but not limited to, Guillain-Barré Syndrome and encephalitis
 - Recurrence of the same Grade 3 toxicity requires discontinuation
- Grade 4
 - Permanently discontinue

6.5.3 Cardiotoxicities of Specific Interest

6.5.3.1 Decreased Left Ventricular Ejection Fraction

Left ventricular ejection fraction (LVEF) will be monitored at regular intervals during the study. If a decrease in cardiac function is suspected, LVEF should be determined using the same method as used prior to treatment.

Specifically, for events of decreased cardiac function, patients will be discontinued from further treatment if either of the following criteria are met:

- $\geq 15\%$ absolute decrease in LVEF from pre-treatment values, or
- LVEF below institutional normal limits (or 50% if no limits are available) and $\geq 10\%$ absolute decrease in LVEF from pretreatment values

6.5.3.2 Myocarditis

- Grade 1 or 2 myocarditis
 - Hold pembrolizumab and margetuximab
 - Based on severity, administer corticosteroids
 - Ensure adequate evaluation to confirm etiology and/or exclude other causes
- Grade 3 or 4 myocarditis
 - Permanently discontinue pembrolizumab and margetuximab
 - Based on severity, administer corticosteroids
 - Ensure adequate evaluation to confirm etiology and/or exclude other causes

6.6 Method of Assigning Patients to Treatment Groups

Patients will be assigned sequentially to the dose escalation cohorts and cohort expansion portions of the study.

6.7 Blinding

This is an open-label study and no blinding will be employed.

6.8 Concomitant Therapy

Margetuximab and pembrolizumab are the only anti-cancer drugs to be administered routinely in this study. No concomitant anti-cancer therapy will be given with exception of adjuvant hormonal therapy for treatment of patients with breast or prostate cancer. All concomitant medications and blood products administered during the patient's participation in the study until the post treatment follow-up visit must be recorded in the source document and on the electronic Case Report Form (eCRF). All changes in infusions, including interruptions and their duration as well as reductions in rate and duration must be recorded.

The following rules concerning concurrent treatment(s) will apply in this study:

- Any other anti-neoplastic therapies including but not limited to chemotherapy or other small molecules, biologics, or radiotherapy are not allowed. For patients who require palliative radiotherapy (i.e., cumulative dose less than 3000 rads, limited field of distribution) for reasons other than disease progression, therapy with margetuximab and/or pembrolizumab may be interrupted for up to 4 weeks. Palliative radiotherapy may not be given concurrently with either margetuximab or pembrolizumab. Treatment with palliative therapy should be initiated at least 24 hours after receiving either margetuximab or pembrolizumab, and re-initiation of margetuximab or pembrolizumab can begin seven (7) days after the completion of palliative radiotherapy if there were no complications associated with the radiotherapy. Palliative radiotherapy fields also should not overlap tumor lesions that have previously been designated as target lesions. In the event that this is medically necessary for palliative purposes, the patient may continue on study, but will no longer be evaluable for objective response from the time palliative radiotherapy is initiated.
- Patients may not receive other investigational drugs during the period of study participation.

- Because margetuximab has the capacity to induce ADCC and pembrolizumab has a mechanism of action dependent upon the engagement of T lymphocytes, the use of corticosteroids should be limited to the extent possible. Chronic doses of corticosteroids in excess of 10 mg daily of prednisone or equivalent is prohibited other than for the management of drug-related adverse experiences. Steroids or other immune suppression therapy may be employed in the treatment of suspected margetuximab or pembrolizumab-associated immune-inflammatory or autoimmune AEs in consultation with the Sponsor. Note: inhaled steroids are allowed for management of asthma.
- The use of other immuno-suppressive agents is prohibited, unless they are being used to treat an adverse event.
- Use of granulocyte colony stimulating factor, granulocyte-macrophage colony stimulating factor or other growth factors is prohibited.
- Live vaccines within 30 days prior to the first dose of trial treatment and while participating in the trial are prohibited. Examples of live vaccines include, but are not limited to, the following: measles, mumps, rubella, chicken pox, yellow fever, rabies, BCG, and typhoid (oral) vaccine. Seasonal influenza vaccines for injection are generally killed virus vaccines and are allowed. However, intranasal influenza vaccines (e.g. Flu - Mist®) are live attenuated vaccines, and are not allowed.

Patients may receive the following concurrent therapy:

- Antiemetics, antidiarrheals, anticholinergics, antispasmodics, antipyretics, antihistamines, analgesics, antibiotics and other antimicrobials, histamine receptor antagonists or proton pump inhibitors, and other medications intended to treat symptoms or signs of disease.
- Transfusions such as red blood cells and platelets are permitted to treat symptoms or signs of anemia or thrombocytopenia and should be documented on the concomitant medication form. IV fluids used for symptomatic treatment/hydration should also be documented on the medication form.
- Use of bisphosphonates or receptor activator of nuclear factor kappa-B ligand (RANK-L) inhibitors is allowed.
- All patients should use highly effective methods of contraception during treatment and for a period of 7 months after discontinuation of treatment. Highly effective birth control includes hormonal contraceptives, intrauterine device or system, vasectomy, or tubal ligation. If a highly effective method is not achievable, then a “double barrier” method is an effective alternative in which the male partner must use a condom with spermicide and the female partner must use a diaphragm or cervical cap concurrently.

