 15. Is not pregnant or breastfeeding or expecting to conceive or father children within the projected duration of the trial, starting with the prescreening or screening visit through 120 days after the last dose of trial treatment.

Tumor Biopsy

16. At least 20 of the 60 patients enrolled in the Cohort Expansion Phase (Part B) under the Original Protocol and Protocol Amendment 1 must have one lesion considered to be potentially accessible to biopsy and be willing to provide consent for biopsy samples. An attempt at a tumor biopsy of locally accessible lesions will be made for at least 20 of the 60 patients. Tumor lesions used for biopsy should not be lesions used as RECIST target lesions unless there are no other lesions suitable for biopsy. If a RECIST target lesion is used for biopsy, the lesion must be ≥ 2 cm in longest diameter. Tumor biopsies should only be obtained from lesions that are felt to be accessible with acceptable clinical risk in the judgment of the investigator and should not be lesions used as RECIST target lesions, unless there are no other lesions suitable for biopsy. If a RECIST target lesion is used for biopsy, the lesion must be ≥ 2 cm in longest diameter. Lesions to be biopsied should not have been previously irradiated, unless the lesion has grown in size beginning at least 14 days since the last radiation dose. Note that multiple lesions may be used to obtain the biopsy sample.
 - The 25 patients enrolled into Part C will not be required to have pre- and on-treatment biopsies.
 - Diagnostic biopsy sample performed as standard of care will be collected from all patients on study. Patients enrolled on this study will be required to have an identified archival tumor specimen.

Previous Checkpoint Inhibitor Therapy

17. Patients who have previously received an immune checkpoint inhibitor (e.g., programmed-death ligand 1 antibody [anti-PD-L1], programmed cell death protein 1 antibody [anti-PD-1], cytotoxic T-lymphocyte-associated protein 4 antibody [anti-CTLA-4]) prior to enrollment must have toxicities related to the checkpoint inhibitor resolved to \leq Grade 1 or baseline (prior to the checkpoint inhibitor) to be eligible for enrollment.

Exclusion Criteria:

1. Patients with symptomatic central nervous system (CNS) metastases must have been treated, be asymptomatic, and meet the following at the time of enrollment:

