2.5.1.2 Margetuximab

The dose for margetuximab in the Dose Escalation Phase (Part A) will begin at 10 mg/kg IV (120-minute infusion), with a proposed escalation to 15 mg/kg, given on a once every 3-weeks schedule. There will be a dose de-escalation to 6 mg/kg margetuximab if the starting dose of 10 mg/kg in combination with pembrolizumab is found to exceed the MTD.

The initial margetuximab dose proposed, 10 mg/kg, is based on the PK and safety profile of margetuximab from the two ongoing clinical studies.

Clinical PK were evaluated in the Phase 1 study. A two-compartment model with parallel linear and Michaelis-Menten elimination adequately described the observed (interim) data. Model parameters were generally in agreement with those commonly expected for a monoclonal antibody. Single dose exposure was predicted to be approximately dose proportional at doses > 3 mg/kg when dosed weekly for 3 weeks in 4-week cycles and \geq 15 mg/kg when dosed every 3 weeks. The terminal half-life was estimated at 12.7 days.

Table 1 Margetuximab Pharmacokinetics at Steady State – 6 mg/kg, 10 mg/kg, 15 mg/kg, 18 mg/kg – CP-MGAH22-01

Parameter (unit)	Margetuximab Dose and Schedule				
	6 mg/kg QW ^a N=19	10 mg/kg Q3W ^b N=6	15 mg/kg Q3W ^b N=6	18 mg/kg Q3W ^b N=6	
C_{trough} ($\mu\text{g/mL}$)	Mean	73.0	42.3	69.9	86.1
	(SD)	(38.2)	(25.5)	(42.9)	(47.9)
	Median (95% CI)	66.9 (20.5 - 169)	37 (6.86 – 101)	61 (15.8 - 180)	77.6 (20.8 - 207)
C_{max} ($\mu\text{g/mL}$)	Mean	217	236	360	429
	(SD)	(58.1)	(16.8)	(93.9)	(103)
	Median (SD)	211 (125 - 355)	227 (136 – 380)	345 (222 - 590)	417 (263 - 660)
AUC ($\mu\text{g/mL}\cdot\text{h}$)	Mean	84700	49500	72200	87500
	(SD)	(30000)	(16500)	(27200)	(30300)
	Median (95% CI)	80500 (40700 - 15800)	43100 (20400 – 84400)	66800 (35300 - 139000)	82200 (43600 - 160000)

a Dosed once weekly (QW) for 3 weeks in 4-week (28-day) cycles

b Dosed once every 3 weeks in 3-week (21-day) cycles.

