5.1 Inclusion Criteria

General:

1. Ability to provide informed consent and documentation of informed consent prior to initiation of any study-related tests or procedures that are not part of standard-of-care for the patient's disease. Patients must also be willing and able to comply with study procedures, including the acquisition of specified research specimens.
2. Age \geq 18 years old (minimum age dependent upon local regulations).
3. Patients may be male or female.
4. **Sixty patients in Part B:** Have histologically proven unresectable locally advanced or metastatic HER2+ gastroesophageal junction (GEJ) or gastric cancer (GC) determined as 3+ by IHC or 2+ by IHC and in situ hybridization– (ISH-) amplified (≥ 2.0) (as per College of American Pathologists/American Society of Clinical Oncology 2016 Guidelines) in most recent tumor biopsy.

Twenty-five patients in Part C (GC only): As of Amendment 2, up to 25 additional patients will have histologically proven unresectable locally advanced or metastatic HER2+ GC (as defined in AJCC Cancer Staging Manual, 8th Edition) determined as 3+ by IHC (as per College of American Pathologists/American Society of Clinical Oncology 2016 Guidelines) in the most recent tumor biopsy.

5. Have received prior treatment with trastuzumab.
6. Have received treatment with one line of cytotoxic chemotherapy in the metastatic setting, which includes trastuzumab. Prior adjuvant therapy that resulted in relapse within 6 months of completion of therapy will be considered a line of treatment for metastatic disease. Eligible patients must have documented progression on/after the most recent line of therapy. Patients who discontinue trastuzumab for other reasons (e.g., financial) are eligible if they have documented progression on/after trastuzumab without receiving alternate treatment.
 - In Parts B and C, only one prior line of treatment that includes trastuzumab is allowed.
7. Resolution of all chemotherapy or radiation-related toxicities to \leq Grade 1 (with exception of \leq Grade 2 alopecia, stable sensory neuropathy, or stable electrolyte disturbances that are managed by supplementation).

8. Eastern Cooperative Oncology Group (ECOG) performance status of 0 or 1 (**Appendix 6**).
9. Life expectancy \geq 12 weeks.

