10. Measurable disease as per Response Evaluation Criteria in Solid Tumors (RECIST) 1.1 (**Appendix 7**) and documented by computed tomography (CT) and/or magnetic resonance imaging (MRI). Patients with evaluable disease only will not be enrolled on this study. Note: Lesions to be used as measurable disease for the purpose of response assessment must either a) not reside in a field that has been subjected to prior radiotherapy, or b) have demonstrated clear evidence of radiographic progression since the completion of prior radiotherapy and prior to study enrollment.
11. Patients should have a formalin-fixed, paraffin embedded tumor specimen or unstained slides identified and available for analysis, to enable determination of the expression of HER2 and PD-L1 within tumor specimens using IHC staining.

Laboratory Features:

12. Acceptable laboratory parameters as follows:
 - a. Platelet count $\geq 100 \times 10^3/\mu\text{L}$ without transfusion within 2 weeks prior to the initiation of study drug.
 - b. Absolute neutrophil count (ANC) $\geq 1.5 \times 10^3/\mu\text{L}$ in the absence of any growth factor support within 2 weeks prior to the initiation of study drug.
 - c. Hemoglobin (Hgb) ≥ 9 g/dL.
 - d. ALT/AST $\leq 3.0 \times \text{ULN}$; for patients with hepatic metastases, ALT and AST $\leq 5 \times \text{ULN}$.
 - e. Total bilirubin $\leq 1.5 \times \text{ULN}$, except patients with Gilbert's syndrome, who may enroll if the conjugated bilirubin is within normal limits.
 - f. Creatinine < 2 mg/dL, or a calculated or measured creatinine clearance > 50 mL/min.

Reproductive Features:

13. Female patients of childbearing potential (not surgically sterilized and between menarche and 1 year postmenopause) must have a negative urine pregnancy test performed within 72 hours prior to the initiation of study drug administration. Further, female patients of childbearing potential must agree to use highly effective contraceptive measures from the time of consent through 120 days after discontinuation of study drug administration.

For Canadian patients only: Female patients of childbearing potential must have a negative pregnancy test prior to every cycle of pembrolizumab.

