- Highly effective methods of contraception include hormonal contraceptives, intrauterine device or system, vasectomy, or tubal ligation. If a highly effective method is not achievable then a “double barrier” method is an effective alternative in which the male partner must use a condom with spermicide and the female partner must use a diaphragm or cervical cap concurrently.
14. Male patients with partners of childbearing potential must use barrier contraception. In addition, male patients should also have their partners use another method of contraception from the time of consent through 120 days after discontinuation of study drug administration.
 15. Is not pregnant or breastfeeding, or expecting to conceive or father children within the projected duration of the trial, starting with the prescreening or screening visit through 120 days after the last dose of trial treatment.

Tumor Biopsy

16. At least 20 of the 60 patients enrolled in the Cohort Expansion Phase (Part B) under the Original Protocol and Protocol Amendment 1 must have one lesion considered to be potentially accessible to biopsy and be willing to provide consent for biopsy samples. An attempt at a tumor biopsy of locally accessible lesions will be made for at least 20 of the 60 patients. Tumor lesions used for biopsy should not be lesions used as RECIST target lesions unless there are no other lesions suitable for biopsy. If a RECIST target lesion is used for biopsy, the lesion must be ≥ 2 cm in longest diameter. Tumor biopsies should only be obtained from lesions that are felt to be accessible with acceptable clinical risk in the judgment of the investigator.
 - The 25 patients enrolled into Part C will not be required to have pre- and on-treatment biopsies.
 - Diagnostic biopsy sample performed as standard of care will be collected from all patients on study.

Previous Checkpoint Inhibitor Therapy

17. Patients who have previously received an immune checkpoint inhibitor (e.g., anti-PD-L1, anti-PD-1 anti-CTLA-4) prior to enrollment must have toxicities related to the checkpoint inhibitor resolved to \leq Grade 1 or baseline (prior to the checkpoint inhibitor) to be eligible for enrollment.

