17. Any serious underlying medical or psychiatric condition that would impair the ability of the patient to receive or tolerate the planned treatment at the investigational site.
18. Known hypersensitivity to recombinant proteins, polysorbate 80 or any excipient contained in the drug or vehicle formulation for margetuximab or pembrolizumab ([Section 6.1](#)).
19. Vaccination with any live virus vaccine within 4 weeks prior to the initiation of study drug administration. Inactivated annual influenza vaccination is allowed.
20. The female patient who is pregnant or breastfeeding, or expecting to conceive, AND the male patient who is expecting to father children within the projected duration of the trial, starting with the screening visit through 120 days after the last dose of trial treatment.
21. Dementia or altered mental status that would preclude understanding and rendering of informed consent.
22. Employees of MacroGenics, Inc., and Merck & Co., Inc., unless approved by institutional IRB and principal investigator.
23. Prisoners or other individuals who are involuntarily detained.
24. Any issue that in the opinion of the investigator, would contraindicate the patient's participation in the study or confound the results of the study.

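### Post-treatment contraception ends at 120 days in the eligibility criteria and synopsis but at 7 months in Section 6.8, about 93 days later, and nothing says which governs

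*Protocol*

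**What the plan says.** The Protocol gives two end dates for the same precaution.

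**Seven months.** Section 6.8 (Concomitant Therapy) says: "All patients should use highly effective methods of contraception during treatment and for a period of 7 months after discontinuation of treatment". It is the only contraception statement with this period. It is the last item in the list of treatments patients may receive alongside study drug.

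**120 days.** Four eligibility criteria use this period, and the synopsis repeats each one:

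- Section 5.1, inclusion 13: women of childbearing potential "must agree to use highly effective contraceptive measures from the time of consent through 120 days after discontinuation of study drug administration".
- Section 5.1, inclusion 14: "male patients should also have their partners use another method of contraception from the time of consent through 120 days" after stopping study drug. The male patient's own barrier method is in a separate sentence with no end date.
- Section 5.1, inclusion 15 (conception intent): the window runs "through 120 days after the last dose of trial treatment".
- Section 5.2, exclusion 20 (conception intent): the window is "starting with the screening visit through 120 days after the last dose of trial treatment".

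Two pregnancy-reporting rules also use 7 months. Section 7.9.2.6 counts it from the end of treatment, and Section 7.9.5 counts it from completing the trial.

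**The concern.** Inclusion 13 and Section 6.8 cover the same behaviour, overlapping patients and the same starting point, but give different end dates. Neither Section 5 nor the synopsis points to Section 6.8, and no text says which period prevails. All of this is current text in one protocol version.

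Placement makes the shorter period the likelier one to be applied. Sites screen against Section 5, whose criteria are mandatory and allow no exceptions. The longer period is phrased as a recommendation, at the end of a list of permitted medications. A patient who did exactly what inclusion 13 asks would fall short of Section 6.8.

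What is at stake is a reproductive-safety instruction, not a statistical result.

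**Working it through.** The plan states no figure for the gap, so there is none to reproduce. The check is day arithmetic, a count of statements, and a rough pharmacokinetic comparison.

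**Inputs.** 120 days (inclusion 13 to 15, exclusion 20 and the synopsis); 7 months (Section 6.8); month length 365.25/12 = 30.4375 days (the SAP convention, Section 5.1.2); margetuximab half-life, for which Protocol Section 2.5.1.2 says "The terminal half-life was estimated at 12.7 days".

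**Size of the gap (7 months minus 120 days).**

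| Month convention | 7 months (days) | Gap (days) |
|---|---|---|
| SAP, 30.4375 days | 7 × 30.4375 = 213.1 | 213.1 − 120 = 93.1 |
| 30-day months | 7 × 30 = 210 | 210 − 120 = 90 |
| Calendar months | 212 to 215 | 92 to 95 |

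**Count of statements.**

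| Item | Subject | Section 5 | Synopsis |
|---|---|---|---|
| Inclusion 13 | Contraception, women | 120 days | 120 days |
| Inclusion 14 | Contraception, partner's method | 120 days | 120 days |
| Inclusion 15 | Conception intent | 120 days | 120 days |
| Exclusion 20 | Conception intent | 120 days | 120 days |

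That makes 4 × 2 = 8 statements of 120 days, four on contraception and four on conception intent. One contraception statement gives 7 months. Without the synopsis copies and the conception-intent items, the like-for-like comparison is two eligibility items against Section 6.8.

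**Does the half-life settle it?** Assume simple first-order decay at 12.7 days, for margetuximab only:

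- 120 / 12.7 = 9.4 half-lives, leaving about 0.14% (0.5 to the power 9.4).
- 213.1 / 12.7 = 16.8 half-lives.

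This does not suggest that 120 days is unsafe, but it does not establish that 120 days is enough. The half-life comes from interim data. The same section describes a model with parallel linear and saturable elimination, so simple decay is an approximation. Section 2.5.1.1 calls pembrolizumab's half-life long without giving a number. The documents justify neither period for the two drugs together.

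**The case against.** The strongest reply is that the two rules are compatible. Inclusion 13 is an undertaking given at entry, and Section 6.8 is a conduct rule for treated patients. Seven months of use meets both, and inclusion 1 says: "Patients must also be willing and able to comply with study procedures". On a full reading the longer rule contains the shorter one, and no precedence clause is needed. Pregnancies between day 120 and month 7 still fall within the reporting window of Section 7.9.2.6, which acts as a backstop. The eight-to-one tally also overstates the imbalance, since half of it is synopsis copies and half concerns intent. No harm is shown, and 64 patients had already been treated in this study by 30 September 2017 (Section 2.3.1.1), so rewording entry criteria mainly serves later enrolees.

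Much of this stands. Both texts can be met, harm is not demonstrated, and the tally measures how often the shorter period appears, not how severe the problem is. Compatibility, however, helps only a reader who finds the item in Section 6.8. The reporting windows detect pregnancies and do not prevent them. They do not decide which contraception period governs, but they support 7 months as the default.

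**Conclusion.** The concern holds. The Protocol gives two end dates for post-treatment contraception, about 93 days apart (90 to 95 by month convention), and does not reconcile them. The mandatory eligibility text carries the shorter one. Because a site could follow that text exactly and still breach Section 6.8, this is a conflict in a safety rule and not merely missing detail. It should be corrected.

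The conclusion rests on the wording alone and needs no assumption about pharmacology. It does not extend to a claim that 120 days is unsafe. The consent form was not available for review, so what patients were actually told is unknown, and the number affected cannot be computed. No endpoint, sample size or analysis is touched.

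**What to change.** State one post-treatment duration in inclusion 13, 14 and 15, exclusion 20, Section 6.8 and the matching synopsis items. Use 7 months, which satisfies both current texts, unless the sponsor documents that 120 days is sufficient for both drugs. Reword inclusion 14 so that the same end date covers the male patient's own barrier method and his partner's method.

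Check that the consent form carries the chosen period. If 7 months is adopted and the form gave the shorter period, notify patients still within 7 months of their last dose; otherwise no notification is needed.

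The cost is wording in five places in the body plus the synopsis, and one consent-form check. The downside of 7 months is about three more months of contraception for affected patients, which Section 6.8 already asks of them. The statistical analysis does not change.
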